Discuss the research design including but not limited to such issues as: probability of group assignment, potential for subject to be randomized to placebo group, use of control subjects, etc.

This is a cluster randomized trial. We assessed 12 cluster sites for potential eligibility and excluded 4 sites (around Malawi) because they could not provide reliable delivery data. Of the 8 cluster sites chosen, 4 will be randomly allocated to oral health education and xylitol gum and 4 will be allocated to oral health education and no xylitol gum. The randomization will occur as follows: 1. The first site will be randomized, then computer matched by number of deliveries to the non-intervention site. 2. This process will be repeated in sequence until all 8 sites (4 matched sets) are allocated.

Inclusion Criteria:

The following represent our a priori decided upon inclusion criteria: (1) Enrollment at less than or equal to 20 weeks gestation by best obstetrical estimate; or (2) Enrollment post partum with an anticipated next pregnancy within 18 months; or (3) Enrollment preconception with an anticipated pregnancy within 18 months; and (4) Cognitively aware enough to participate in the study; (5) Greater than or equal to 18 years of age (in Malawi, constitutes a legal adult and capacity to consent for study); (6) Willing to participate in the study; (7) Willing to undergo at least two periodontal exams; (8) Willing to chew 1 piece of xylitol gum for 10 minutes after the morning and evening meal (intervention sites); (9) Anticipating to remain within the region for 18 months.

Exclusion Criteria:

(1) Greater than 20 weeks gestation by best obstetrical estimate; (2) Post partum and not anticipating another pregnancy within 18 months; (3) Preconception and not anticipating another pregnancy within 18 months; (4) Not cognitively aware enough to

participate in the study; (5) Not willing to undergo at least two periodontal exams; (6) Less than 18 years of age; (7) Not willing to chew 1 piece of xylitol gum for 10 minutes after the morning and evening meal (intervention sites); (8) Anticipating a move outside of the region within 18 months.

F2. Procedure

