1. Subjects will be recruited by study personnel for potential enrollment during their prenatal visits 2. If enrolled, subjects will be: A) giving medical history/information; B) undergoing a minimum of 2 periodontal exams; (Visit 1 and 2) C) participating in antenatal care; D) chewing xylitol gum (at intervention cluster sites) twice a day following meals; E) undergo delivery (Visit 3) Participants will also be asked to consent to collection of data and potential use of xylitol gum. As previously described, since this product is commercially available over the counter and for the indication of the prevention of dental disease, no IND is necessitated.

Plans for study oversight are as follows: 1. Post-approval, this study will be monitored by the PI and co-PI at BCM in Houston by ensuring that data entry is up to date on a weekly basis. The PI and co-PI will also take regular trips to Malawi to ensure that all study related material is collected and stored according to plan and in compliance with confidentiality requirements. 2. Complaints about the study will be handled by local investigators in Malawi under the guidance of the PI and co-PI at Baylor. 3. Non-compliance on the part of study staff will be addressed by the PI and co-PI. Study staff will be re-educated on study procedures and confidentiality requirements if indicated, and disciplinary action will be taken if appropriate. 4. Unanticipated Problems Involving Risk to Subjects or Others will be handled by local investigators with immediate notification of BCM PIs and co-PIs. Specifically, if there are unanticipated risks or adverse events, then a significant adverse event report will be filed with the Baylor Institutional Review Board and it will also be reported to the Malawi Ministry of Health for evaluation.

Section G: Sample Size/Data Analysis

G1. Sample Size

How many subjects (or specimens, or charts) will be used in this study?

Local: 10360 Worldwide: 10360

Please indicate why you chose the sample size proposed:

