Successful engagement in meaningful global research, and notably a randomized trial, necessitates tremendous up-front leg work and demonstration of feasibility. We have invested three years in preparation for the proposed PPax trial and are confident in having now parsed down the necessary components suggesting that we can execute the proposed trial on budget and on time, that we should execute the proposed study testing xylitol gum as an intervention, and that it will take a cluster randomization design enrolling a total sample size of 9360 subjects at 8 proposed sites to demonstrate effect size.

We have estimated that a total sample size of 9360 subjects will be sufficient to demonstrate a 33% reduction in the primary outcomes of (1) preterm birth <37 and <34 weeks, and (2) associated neonatal morbidity and mortality based upon our prior work in Malawi. In our study design (where the health center serves as the unit of randomization), we have accounted for a 30% loss to follow up and calculated our per site enrollment to necessitate 1170 subjects at each of 8 sites.

G2. Data Analysis

Provide a description of your plan for data analysis. State the types of comparisons you plan (e.g. comparison of means, comparison of proportions, regressions, analysis of variance). Which is the PRIMARY comparison/analysis? How will the analyses proposed relate to the primary purposes of your study?

Intercluster (between cluster) analysis will include univariate and multivariate analyses analyzing the number of clusters, average cluster size, range of cluster size, rate of preterm birth, rate of neonatal complications, rate of periodontal disease, rate of maternal comorbidities, range and variance of each measure; analysis by intention to treat and by multivariate measures with GEE. Intracluster (per subject, by cluster) analysis will include univariate and multivariate analyses analyzing the number of subjects, average gestational age, rate of preterm birth, rate of neonatal complications, rate of periodontal disease, rate of maternal comorbidities, range and variance of each measure; analysis by intention to treat and by multivariate measures with GEE.

Section H: Potential Risks/Discomforts

H1. Potential Risks/Discomforts

Describe and assess any potential risks/discomforts; (physical, psychological, social, legal, or other) and assess the likelihood and seriousness of such risks:

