When research is conducted in collaboration with outside entities or organizations, the PI must obtain the necessary approvals from those entities. The BCM IRB may request documentation that such approvals have been obtained. Please list and describe the planned sites for this multi-site research for which the BCM PI is either Sponsor-Investigator and/or Coordinating Center. Sites that do not meet the requirements for inclusion in section A6a of the protocol summary and BCM informed consent documents should be listed here.

Letters of support from Malawi, stating that the Ministry of Health supports the project, are attached. The IRB Approval Letter from the Ministry of Health is also attached.

Section I: Potential Benefits

Describe potential benefit(s) to be gained by the individual subject as a result of participating in the planned work.

Potential benefits may include a reduction in preterm birth and an improvement in oral health.

Describe potential benefit(s) to society of the planned work.

If comprehensive oral healthcare and chewing xylitol gum indeed reduces the risk of preterm birth, society would benefit from this knowledge.

Do anticipated benefits outweigh potential risks? Discuss the risk-to-benefit ratio.

The benefits to the participants and to society outweigh the minimal risks of this project.

Section J: Consent Procedures

J1. Waiver of Consent

Will any portion of this research require a waiver of consent and authorization?

No

J1a. Waiver of requirement for written documentation of Consent

Will this research require a waiver of the requirement for written documentation of informed consent?

No

J2. Consent Procedures

Who will recruit subjects for this study?

PI
PI's staff

Describe how research population will be identified, recruitment procedures, any waiting period between informing the prospective participant and obtaining consent, steps taken to minimize the possibility of coercion or undue influence and consent procedures in detail.

The research population will be drawn from eight clinical sites, all in the greater Lilongwe region of Malawi (a 54 km urban-rural region surrounding Lilongwe). Through BIPAI, TCH and BCM have had a continual presence in this region since 2007 and we have been partnered in this region for obstetrical care since 2011.

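### Section G1 enters 10360 subjects, but the justification beneath it supports 9360 (8 sites × 1170), and the extra 1000 are not explained

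*Combined protocol and SAP*

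**What the plan says.** Section G1 of the combined protocol and SAP has two prompts in sequence. The first asks "How many subjects (or specimens, or charts) will be used in this study", and the entry is "Local: 10360 Worldwide: 10360". The second says "Please indicate why you chose the sample size proposed", so the text that follows should defend the number just entered.

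That text instead describes a cluster-randomised design "enrolling a total sample size of 9360 subjects at 8 proposed sites to demonstrate effect size". It then repeats the total with the effect attached: "We have estimated that a total sample size of 9360 subjects will be sufficient to demonstrate a 33% reduction in the primary outcomes". Finally it gives the breakdown by site: "we have accounted for a 30% loss to follow up and calculated our per site enrollment to necessitate 1170 subjects at each of 8 sites".

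The number of sites is the same elsewhere. Section F1 states "Of the 8 cluster sites chosen, 4 will be randomly allocated to oral health education and xylitol gum", with the other four as controls, and section J2 states "The research population will be drawn from eight clinical sites, all in the greater Lilongwe region of Malawi". The figure 10360 does not appear again.

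**The concern.** The number entered as the study size is not the number that is justified. A single form item poses the question and the reason for the answer, and the two differ by a round 1000.

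The count field is the plan's direct statement of how many women will be enrolled. Anyone who takes it as the target plans for 1000 women whom the justification does not call for, each asked for at least two periodontal examinations under section F. The plan also leaves open whether enrolment is complete at 9360 or at 10360. Section H3 foresees statistical analysis on data as they accumulate, so the end of enrolment should be fixed beforehand. What is at stake is a consistent, justified target; power is not shown to suffer.

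**Working it through.** **Inputs, all from section G1 unless noted**

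- Count field: 10360 local, 10360 worldwide.
- Total in the justification: 9360.
- Enrolment per site: 1170, with 30% loss to follow-up already included.
- Sites: 8, four per arm (F1; also eight in J2).

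**Reproducing the plan's figure**

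- Sites × enrolment per site = 8 × 1170 = 9360. This matches the justification exactly and does not match the count field.
- Gap: 10360 − 9360 = 1000. Relative size: 1000 / 9360 = 10.7%.

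**What 10360 would imply with equal sites**

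- Per site: 10360 / 8 = 1295, which is 1295 − 1170 = 125 more than stated.
- Per arm: 4 × 1295 = 5180 against 4 × 1170 = 4680, a difference of 500.

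**Can loss to follow-up link the two totals?**

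- Applying 30% again to 9360 gives 9360 / 0.7 = 13372 (rounded up) or 9360 × 1.3 = 12168. Neither is 10360.
- If 9360 was reached by multiplying by 1.3, the starting number was 9360 / 1.3 = 7200, and the other convention would give 7200 / 0.7 = 10286 (10288 if rounded up per site). This comes within 74 (or 72) of 10360 but does not equal it, and 7200 is not in the document.

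**Can something else explain the extra 1000?**

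- *Another site.* Three sections say eight. Also, 10360 / 1170 = 8.85, so a further site of the planned size would not produce 10360.
- *Specimens.* Section N records no sample collection.
- *Infants.* E5 and J4 both answer no to enrolling children.
- *A ceiling, a screening surplus or a count of charts.* None is stated with a number.

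**Could the 33% claim simply be moved to 10360?** Not without new work. With 8 clusters fixed, more women per cluster add less than proportional information. The document gives no intracluster correlation (ICC), so the values here are assumptions. With retained women per site m = 1170 × 0.7 = 819, or 1295 × 0.7 = 906.5, and effective size per site m / (1 + (m − 1) × ICC):

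| Assumed ICC | m = 819 | m = 906.5 | Gain |
|---|---|---|---|
| 0.001 | 450.5 | 475.7 | 5.6% |
| 0.01 | 89.2 | 90.2 | about 1% |
| 0.05 | 19.55 | 19.59 | 0.2% |

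Enrolment would rise by 10.7% in every row.

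**The case against.** The strongest reply is that this is an inconsistency without a demonstrated harm. The larger figure is in the count field, so it cannot lead to under-enrolment; the working instruction of 1170 at each of 8 sites is explicit; and no analysis depends on 10360. That is right as far as it goes, and no threat to power or validity is claimed here.

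A second reply is that the document does not show which number is the mistake. The field may have been raised after the justification was written, in which case reducing it to 9360 would undo an intended increase. This stands as a caution, and it is why the fix keeps a route for an intended 10360.

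Third, the elimination of other explanations is not complete. The field covers specimens and charts as well as subjects, section K confirms that health-record data are used, and Aim 1 in section D follows small infants to 30 days. Equal local and worldwide entries do not by themselves exclude another site, and the 8.85 calculation assumes that such a site would enrol 1170. The form also refers to an attached summary and a manual of procedures that are not available here. All true, but none of these supplies a count that turns 9360 into 10360.

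Last, 9360 rests on one product, and it cannot be derived from first principles because the significance level, power, baseline rate and ICC are not given. That is a separate gap. It does not reconcile the two totals.

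**Conclusion.** The concern holds. The entered sample size exceeds the size its own justification supports by 1000 women, or 10.7% of 9360, and the available text does not explain the excess. The conclusion needs only the stated figures and one multiplication. The figures of 1295 per site and 5180 per arm additionally assume equal sites. Calling 9360 the justified number means that it is the total given in the justification, agrees with the site arithmetic and carries the 33% claim; it does not mean that the underlying power calculation has been verified. Whether 10360 is a slip or an unrecorded increase cannot be told from the document. It must be corrected because a stated sample size should not be contradicted by the paragraph that defends it, and only the sponsor can settle it.

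**What to change.** Enter 9360 for both local and worldwide in the G1 count field. This changes one number and brings the field into line with 1170 at each of 8 sites and with the total to which the 33% reduction is attached.

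If the sponsor does intend 10360, take one of two routes:

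- State in G1 what the additional 1000 are, for example an upper limit or a different counting unit, and keep 9360 as the justified sample size. This costs one sentence.
- Make 10360 the target: revise enrolment to 1295 per site (equal sites) and redo the justification rather than carry the 33% claim over unchanged. This costs a new sample size calculation and 125 more women at each of 8 sites.

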
Section D: Purpose and Objectives

Our overarching hypothesis is that comprehensive primary preterm birth prevention, inclusive of maternal oral health with xylitol chewing gum (the intervention), will reduce the rate of periodontal disease and caries, preterm birth prevalence, and neonatal mortality. We propose two aims to test our hypothesis: *1* Aim 1 (primary outcome). Our primary aim will be to determine the impact of xylitol gum on the (1) rate of preterm birth <37 and <34 weeks gestation, (2) rate of <2000 gram infants, (3) rate of survival of <2000 gram infants to 30 days, and (4) composite neonatal morbidity of <2000 gram infants at 30 days of age. *2* Aim 2 (secondary outcome). Xylitol chewing gum has been demonstrated by other investigators to prevent otitis media (double blind, randomized controlled trial (RCT), and maternal consumption prevents dental decay in children up to 5 years of age, even when the children did not chew the gum (RCT). In Malawi, where running water and inadequate dental care are realities of everyday life, we will determine whether use of xylitol gum will decrease the prevalence of (1) periodontal disease, and (2) caries among gravidae.

Section E: Protocol Risks/Subjects

E1. Risk Category

Category 1: Research not involving greater than minimum risk.

E2. Subjects

Gender:

Female

Age:

Adult (18-64 yrs)

Ethnicity:

All Ethnicities

Primary Language:

Chichewa

Groups to be recruited will include:

Both patients and healthy, non-patient, normals

Which if any of the following vulnerable populations will be recruited as subjects?

Pregnant women, Women of child bearing potential

Vulnerable populations require special protections. How will you obtain informed consent, protect subject confidentiality, and prevent undue coercion?

Please see Section J.

E3. Pregnant woman/fetus

Will pregnant women and/or fetuses (as described in 45 CFR 46 Subpart B) be enrolled in the research?

Yes

E4. Neonates

Will neonates of uncertain viability or nonviable neonates (as described in 45 CFR 46 Subpart B) be enrolled in the research?

No

E5. Children

Will children be enrolled in the research?

No

Section F: Design/Procedure

F1. Design

Select one category that most adequately describes your research:

z.r) Randomized, Efficacy Study -- Surgical Techniques/Interventions

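### Five measures are labelled primary in Aim 1, G1 lists a different primary set, and G2 names no primary comparison, alpha or multiplicity rule; the inputs needed to check the size claim are not shown

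*Combined protocol and SAP*

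**What the plan says.** Section D labels Aim 1 as the primary outcome. It opens "Our primary aim will be to determine the impact of xylitol gum on the (1) rate of preterm birth <37 and <34 weeks gestation", continues with "2) rate of <2000 gram infants, (3) rate of survival of <2000 gram infants to 30 days" and ends with "composite neonatal morbidity of <2000 gram infants at 30 days of age". Because the first item holds two gestational cut-offs, that makes five measures.

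G1 states that 9360 women are "sufficient to demonstrate a 33% reduction in the primary outcomes of (1) preterm birth <37 and <34 weeks, and (2) associated neonatal morbidity and mortality". The only source it offers for this estimate is the remark that it is "based upon our prior work in Malawi". It also gives 30% loss to follow-up and 1170 women at each of 8 sites. The form field above that text reads "Local: 10360 Worldwide: 10360".

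The G2 form asks "Which is the PRIMARY comparison/analysis". The answer lists between-cluster and per-subject analyses, each univariate and multivariate, of preterm birth (no cut-off given), neonatal complications, periodontal disease and maternal comorbidities. It closes each list with "analysis by intention to treat and by multivariate measures with GEE". Neither the under-2000 g birth rate nor 30-day survival appears there.

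**The concern.** Three sections that should carry one outcome list do not. G1 drops the under-2000 g rate, and its neonatal item has neither the weight restriction nor the 30-day time point. G2 adds an Aim 2 outcome, periodontal disease, alongside the others and ranks nothing.

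Two things are at stake. A positive result on any of several measures, from any of several models, could be reported as meeting the primary aim. Conversely, a non-significant result on a rarer outcome could be read as no effect, although the plan shows no power for it.

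**Working it through.** **The plan's own figure.** 8 × 1170 = 9360, so the total agrees with the per-site number. It cannot be derived from what is stated, because control rate, ICC, alpha and power are missing. For scale, take an assumed 9.6% control rate (the worldwide figure in Section C, not a stated design value), a relative reduction of 33%, two-sided 5% and 80% power. The usual two-proportion formula then needs 1153 per arm without clustering. After 30% loss, 9360 leaves 9360 × 0.70 / 2 = 3276 per arm. The implied design effect is 3276 / 1153 = 2.84. With 1170 × 0.70 = 819 per site, the implied ICC is (2.84 − 1) / 818 ≈ 0.0023. At an assumed 15% control rate the need is 701 per arm, the design effect 4.67 and the ICC about 0.0045. So 9360 could be adequate for birth before 37 weeks; the document does not let a reader tell.

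**False positives.** Assume each outcome is tested at two-sided 5% and any positive result counts. For k independent tests the rate is 1 − 0.95^k. For correlated tests it was simulated with equicorrelated normal statistics (10^6 draws).

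| Outcomes | Independent | Correlation 0.5 | 0.7 | 0.9 |
|---|---|---|---|---|
| Five (Aim 1) | 22.6% | 18% | 15% | 10% |
| Three (G1, neonatal item as one composite) | 14.3% | 13% | 11% | 8% |

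This covers outcomes only. The choice between univariate and multivariate, and between cluster-level and per-subject analysis, would add to it and is not quantified here.

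**Power.** Let p1 be the control rate and p2 = 0.67 p1, with 3276 evaluable deliveries per arm and DE = 1 + 818 × ICC. Then SE = √[(p1(1−p1) + p2(1−p2)) × DE / 3276]. The ratio (p1 − p2)/SE is referred to a normal distribution, or to a noncentral t with 6 df (eight unpaired sites).

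Worked case, birth before 37 weeks at 9.6% and ICC 0.001: p2 = 0.0643, DE = 1.818, SE = 0.00903, ratio = 0.03168 / 0.00903 = 3.51. Normal power is Φ(3.51 − 1.96) = 94%; with 6 df it is 83%.

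Birth before 34 weeks is taken as 20–40% of birth before 37 weeks (assumed), so p1 runs from 1.92% to 3.84%. The ratio is then 1.51 to 2.16 at ICC 0.001 and 0.91 to 1.29 at ICC 0.005.

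| Outcome (base 9.6%) | ICC 0.001: normal / 6 df | ICC 0.005: normal / 6 df |
|---|---|---|
| Before 37 weeks | 94% / 83% | 55% / 42% |
| Before 34 weeks | 33–58% / 25–44% | 15–25% / 12–19% |

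If the four matched sets are analysed as pairs (3 df, no variance gain assumed), birth before 37 weeks has 65% at ICC 0.001 and 31% at 0.005. At an assumed 15% control rate it has 99% (normal) or 96% (6 df) at ICC 0.001, and 77% or 61% at 0.005. Using 10360 instead of 9360 gives 10360 × 0.70 / 2 = 3626 per arm and adds at most about 2 points to the figures for birth before 37 weeks.

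**The case against.** The strongest reply is that the plan is less bare than it looks. G1 does state an effect size, a loss rate and the cluster layout, and it points to earlier Malawi data. A reader might infer that the size claim has no inputs at all; that is not so. What is absent is the set needed to check it. The document is an ethics application that refers to a protocol and an attached summary, so these inputs may exist elsewhere. The fair statement is that they are not shown here.

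G1's neonatal item may also be shorthand for the two Aim 1 outcomes in under-2000 g infants. On that reading the only difference between the lists is the under-2000 g birth rate. This narrows the mismatch but does not supply a primary comparison.

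Nothing in the plan says that any single positive result means success. If all outcomes had to succeed, there would be no inflation. The 10–23% is therefore conditional on that reading, and its lower end depends on the correlation chosen.

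It is tempting to say that birth before 34 weeks always has less power. That needs a common ICC: with the normal test at 9.6%, birth before 34 weeks at a 40% share and ICC 0.001 has 58%, above the 55% for birth before 37 weeks at ICC 0.005.

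Finally, G2 already plans intention to treat and GEE, so clustering is not ignored. That stands, but neither says which outcome or model decides success.

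**Conclusion.** The point holds. Five measures carry the primary label in Section D, G1 uses a different set, and G2 does not answer the question about the primary comparison or set any error rule. The false-positive rate could be about two to four and a half times the nominal 5%, if any positive counts.

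That 9360 suffices for every outcome G1 lists is not demonstrated. A reader might infer that 9360 is too small or wrong; the documents do not support that, since under some plausible rates and ICCs it is enough for birth before 37 weeks. What can be said is that, at a common ICC, the same number gives less power for its rarer subset, birth before 34 weeks.

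All power figures rest on assumed control rates, shares and ICCs. They also treat every retained woman as an evaluable delivery. F1 admits preconception and postpartum women who only anticipate a pregnancy, and G1 does not say whether the 30% covers those who never conceive. If it does not, the figures are optimistic.

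**What to change.** 1. Use one outcome list in Section D, G1 and G2. Make preterm birth before 37 weeks the single primary outcome: it is listed first in both places and contains the earlier cut-off. Test it at two-sided 5% by one named intention-to-treat comparison that accounts for the 8 clusters. GEE with a small-sample correction, or a t-test on site rates, would each do. State whether the four matched sets enter the analysis.
2. Make preterm birth before 34 weeks, then the rate of under-2000 g infants, key secondary outcomes, tested in that order only while each previous test is significant. Report 30-day survival and composite morbidity among under-2000 g infants as descriptive or supportive, because that denominator is itself an outcome the gum may change. Label all other analyses supportive.
3. Limit the 33% statement to preterm birth before 37 weeks, and state the Malawi control rate, ICC, alpha and power at which it holds.

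The cost is wording plus a short recalculation from data the sponsor says it has. Four outcomes lose primary status, a non-significant primary result blocks the later tests, and the size claim narrows and may not hold: at 9.6%, 80% power needs an ICC no higher than about 0.0023 (normal) or 0.0012 (6 df). Splitting 5% evenly over the five outcomes would avoid the blocking. At 1% each, however, power for birth before 37 weeks at 9.6% and ICC 0.001 falls from 94% to 82% (normal) or from 83% to 50% (6 df), and the two outcomes confined to under-2000 g infants would remain confirmatory.

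### The sample size is counted in enrolled women with only a 30% loss-to-follow-up allowance, yet two of three entry routes admit women who are not pregnant, so 9360 is not shown to be enough deliveries

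*Combined protocol and SAP*

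**What the plan says.** F1 (Inclusion Criteria) has three alternative entry routes. One is pregnancy at 20 weeks or less. The other two do not require a current pregnancy: "2) Enrollment post partum with an anticipated next pregnancy within 18 months" and "3) Enrollment preconception with an anticipated pregnancy within 18 months". J2 confirms recruitment on the postpartum ward and before conception, as well as at antenatal booking. F2, by contrast, mentions recruitment only at prenatal visits, followed by antenatal care and delivery as Visit 3.

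Section D defines the Aim 1 outcomes: preterm birth before 37 and 34 weeks, infants under 2000 g, and survival and morbidity of those infants at 30 days. None can be observed without a birth.

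G1 says: "We have estimated that a total sample size of 9360 subjects will be sufficient to demonstrate a 33% reduction in the primary outcomes". It says the investigators "calculated our per site enrollment to necessitate 1170 subjects at each of 8 sites", and the only attrition term is in the statement that "we have accounted for a 30% loss to follow up and calculated our per site enrollment". The form field at the head of G1 gives a different total: "Local: 10360 Worldwide: 10360". Neither the extra 1000 nor the make-up of the 30% is explained.

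G2 plans intention-to-treat and multivariate GEE analyses. Its per-subject list includes "analyzing the number of subjects, average gestational age, rate of preterm birth". It gives no rule for women who have no pregnancy.

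**The concern.** A woman who enters postpartum or preconception, stays in contact and never conceives is not lost to follow-up in the ordinary sense. She counts toward her site's 1170 but supplies no Aim 1 outcome. No passage replaces such women, limits these routes or ties the site target to pregnancies. A site could therefore complete enrolment with fewer deliveries than a 30% deduction suggests, and the plan gives no way to tell.

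A second, smaller issue is comparability. The trial has no placebo (O1), willingness to chew gum is an entry criterion only at intervention sites (F1), and there are four sites per arm. The mix of pregnant, postpartum and preconception recruits could therefore differ between arms. The plan does not name entry route as a covariate, although it is known at enrolment.

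**Working it through.** **Inputs from the documents.** 1170 per site, 8 sites, 30% loss, 33% reduction (G1); 10360 (G1 form field); 4 v 4 sites (F1); 9.6% preterm births worldwide (Section C).

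**Assumed inputs, not in the documents.** s = share enrolled while not pregnant; c = share of those women who conceive and deliver; control preterm rate 9.6%; the 33% taken as relative (risk ratio 0.67); ICC 0.002 or 0.005; two-sided 5% test.

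**1. The plan's own figure.** 1170 x 8 = 9360. The multiplication reproduces. The size itself cannot be rebuilt, because G1 gives no alpha, power, control rate or ICC.

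**2. Evaluable women implied.** If the allowance was N/(1 - 0.30), then 1170 x 0.70 = 819 per site and 9360 x 0.70 = 6552. But 900 x 1.3 = 1170 fits equally well. On that reading 900 per site was intended, and 819 is already 9% short (819/900 = 0.91) before any non-conception. The rest uses 819.

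**3. Deliveries if the 30% leaves out non-conception.**
Deliveries = 6552 x f, with f = 1 - s(1 - c). Enrolment per site to restore 819 = 1170/f.

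| s | c | f | Deliveries (per site) | Shortfall | Enrolment needed per site (total) |
|---|---|---|---|---|---|
| 0 | any | 1 | 6552 (819) | 0 | 1170 (9360) |
| 25% | 80% | 0.95 | 6224 (778) | 5% | 1232 (9856) |
| 50% | 80% | 0.90 | 5897 (737) | 10% | 1300 (10400) |
| 50% | 50% | 0.75 | 4914 (614) | 25% | 1560 (12480) |
| 75% | 50% | 0.625 | 4095 (512) | 37.5% | 1872 (14976) |

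**4. If the 30% is meant to cover both.** The true loss it leaves room for is 1 - 0.70/f: 26% (f = 0.95), 22% (f = 0.90) and 7% (f = 0.75). At f = 0.625, non-conception alone (37.5%) exceeds 30%, so the allowance could not cover it.

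**5. If 10360 is the true total.** 10360 x 0.70 = 7252. Multiplying by f gives 6889 (above 6552), 6527 (0.4% short), 5439 (17% short) and 4533 (31% short) for the four mixes. The extra 1000 absorbs overall non-conception up to 1 - 9360/10360 = 9.7%.

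**6. Effect on power.** Design effect = 1 + (m - 1) x ICC, with m deliveries per site.

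| Deliveries per site | Power, ICC 0.002 | Power, ICC 0.005 |
|---|---|---|
| 819 | 83% | 55% |
| 737 | 81% | 54% |
| 614 | 78% | 53% |
| 512 | 75% | 51% |

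The loss is damped because the design effect falls with m. At ICC 0.002, 819/2.64 = 310 effective deliveries per site become 512/2.02 = 253, a drop of about 18% against 37.5% in the raw count. These figures use a normal approximation. With a t reference on 6 degrees of freedom (8 clusters less 2 arms), the ICC 0.002 column runs from 68% to 60%: a lower level, but a similar drop.

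**The case against.** The strongest reply is that no shortfall has been demonstrated. G1 states no delivery target, loss to follow-up is undefined, and 30% is generous enough that it could include women who never conceive. The 6552 baseline depends on how the allowance was applied. F2, the only step-by-step procedure, recruits at prenatal visits, so few non-pregnant women may be expected. The 10360 field might be the true total. All of this stands, and it rules out the flat conclusion that the design will fall short. It does not show that 9360 is sufficient. No passage says the 30% covers non-conception, J2 contradicts F2 on where women are recruited, and the extra 1000 has no stated purpose.

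A reader might also infer that G2 keeps never-pregnant women in the denominator as women without preterm birth, so that a difference in recruitment mix could imitate a gum effect. The documents do not support that. In G2 the number of subjects and the preterm rate are separate items in a list, with mean gestational age, which exists only for pregnancies, between them. Section C counts preterm birth per births. The denominator is simply unstated, which warrants a clarifying sentence and no more.

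Finally, the power loss is modest, and multivariate GEE is already planned. Both are fair, and they lower the weight of the point.

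**Conclusion.** The sufficiency claim in G1 is made for enrolled women and is not shown to hold for deliveries, which are what Aim 1 needs. The possible shortfall runs from zero to about 37.5% of 6552 over the mixes considered. It is zero if few non-pregnant women are enrolled or if the 30% truly covers non-conception, and smaller if 10360 is the real total. The non-zero figures rest on assumed s and c and on the N/(1 - 0.30) reading. The power cost is at most about 8 points in these scenarios (83% to 75%), at an assumed 9.6% control rate and ICC 0.002, and about 4 points at ICC 0.005.

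This is a gap in the size justification and in the analysis specification. It should be corrected, but it does not by itself undermine the trial.

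**What to change.** - **Restate G1 in deliveries.** Give the required deliveries per site, the expected split by entry route, the share expected to conceive and deliver, and separate terms for non-conception and loss to follow-up. Correct the sufficiency claim to match. Reconcile 9360 with 10360, and the recruitment text in F2 with J2.
- **Add entry route to the GEE** (pregnant, postpartum, preconception) as a named covariate. Add a supporting analysis in women pregnant at enrolment, a group whose membership does not depend on later conception.
- **As a safeguard, fix the denominator and the status codes.** State that preterm and under-2000 g rates are per birth in enrolled women, and record completion without pregnancy separately from loss to follow-up.

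The cost is protocol wording, one status code, one covariate known at enrolment and slightly more analysis work. The stated number of usable deliveries may become less favourable. These changes add no visits or participants. If the restated G1 shows too few deliveries, the sponsor must either accept the weaker claim or enrol more women, which is a separate decision.
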